
[name] was promoted to Clinical Research Coordinator and helped to transition the study into a clinical program embedded with the University of Pennsylvania Health System and the Corporal Michael J. Crescenz Veterans Affairs Medical Center. Additionally, [name] has worked as a clinical research coordinator on a behavioral science study in which he was responsible for reviewing literature and identifying useful survey instruments; developing study protocols; creating a research database and manual; meeting with clinic staff; supervising staff; and corresponding with the Institutional Review Board. [name] will work closely with [name] to oversee the day-to-day aspects of the study. Specifically, he will develop and maintain eligibility lists for recruitment purposes; coordinate and maintain IRB approval for the study; manage the tracking database of outcomes; supervise the work of the research assistant; assist with writing reports and correspondence with Commonwealth Fund; and coordinate quarterly meetings with all study team staff. The research assistant will have a minimum college education and will undergo a 1-week training which covers topics including survey interviewing, data entry, HIPPA and Human Subjects training. The research assistant will be responsible for interfacing with Way to Health platform, recruiting and enrolling patients, verbally administering the baseline and follow-up surveys, monitoring adherence and lottery, tracking laboratory results, and entering outcomes data.

Characteristics of the Study Population

Target population

Diabetes patients of low socioeconomic status living in high poverty zip codes of West/Southwest Philadelphia.

Subjects enrolled by Penn Researchers

150

Subjects enrolled by Collaborating Researchers

0

Accrual

We will enroll 150 patients (50 in each arm) from the Penn Rodebaugh Diabetes Center at the Perelman Center for Advanced Medicine.

Key inclusion criteria

Key inclusion criteria: We will enroll patients who meet the following eligibility criteria: 1) Penn Medicine patients diagnosed with diabetes mellitus (based on ICD-10CM codes from the year prior to study enrollment); 2) glycosylated hemoglobin 9% within the past 6 months; 3) requires insulin; 4) uninsured/publicly insured; 5) residents of high-poverty ZIP codes in West/Southwest Philadelphia; 6) have access to a cellphone with unlimited text message capabilities; 7) greater than or equal to 18 years of age.

Key exclusion criteria

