
the correct phone number using contact verification technology. Step Five: Labs 1. Walk the patient to the laboratory to have their blood drawn for HbA1c evaluation. 2. Provide the patient with a gift card and half page sheet with payment information Step Six: How to Use the Glucometer 1. Provide the patient with a glucometer if they don't already have one. 2. Review the user guide with the patient and answer any questions they may have about using their glucometer. 3. Reinforce/explain to the patient not to delete their glucose reading log from the glucometer because we will extract the log from the glucometer at subsequent visits. Abnormal Blood Glucose Safety Protocol: The study clinician will be notified by the way to health platform if participants glucose is either extremely low or high (60 or 400 mg/dL) and respond accordingly. The study clinician will contact these patients to address the issue. Step Seven: CHW escalation 1. The way to health platform will notify the study team of any individuals who have low adherence (no self-monitoring) or elevated glucose readings (300 mg/dL) for 30% of days over any 2 week period in the first 12 weeks of the study. These individuals will be assigned to receive ongoing CHW support for the duration of the 24-week study period 2. The study team should notify the CHW and send them the patients redcap ID. The CHW will follow up with the patient in 1-2 days. Step Eight: 3 Month Follow Up 1. One month prior, contact the patient to set a date/time for their 3 month follow up appointment. (If patients are unable to be reached, then we will send a letter to their home requesting that they contact us to set up a follow-up appointment.) 2. At the appointment, obtain the blood glucose log of readings from the patients glucometer. 3. Provide the patient with a gift card. Follow up visit is concluded. 4. The window to complete all 3-month follow-up procedures may be extended in cases where patients were prevented from completing visits within the original window due to COVID-19 restrictions. Step Nine: 6 Month Follow Up and Labs 1. One month prior, contact the patient to set a date/time for their 6 month follow up appointment. (If patients are unable to be reached, then we will send a letter to their home requesting that they contact us to set up a follow-up appointment.) 2. At the appointment, obtain the blood glucose log of readings from the patients glucometer. 3. Administer the follow up redcap survey 4. Walk the patient to the laboratory to have their blood drawn for HbA1c evaluation. 5. Provide the patient with a gift card. Follow up visit is concluded. 6. The window to complete all 6-month follow-up procedures may be extended in cases where patients were prevented from completing visits within the original window due to COVID-19 restrictions. Any Engage Study patients screened for recruitment into routine care community health worker programs at Penn Medicine will have their enrollment deferred until their study participation is complete. We will track all screened patients that are deferred because of Engage Study participation and contact them afterwards to offer enrollment into our routine care community health worker program. You may also be contacted during this study as a part of our quality review. If this happens you will just be asked a few questions about how the study has been going and your experiences with the steps listed above.

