risk of low adherence and a linear regression model to obtain the between-arm difference in change in glycosylated hemoglobin. We will adjust these models for any unbalanced baseline covariates to increase efficiency. For exploratory purposes, we will do a per protocol analysis focusing on the subgroup of patients in the hybrid intervention who actually received CHW support, as compared to the patients in the DHI alone arm who would have received support based on low adherence or elevated glucoses. We will also explore predictors of adherence and glycosylated hemoglobin across all three arms. Sample size calculations Based on a similar 24-week trial, we assume that the adherence rate in the usual care arm will be 40% and the rate in the hybrid intervention will be 80%. In the prior trial, the adherence rate in the usual care arm was 47%; however this trial had a lower risk population (higher income and lower baseline glycosylated hemoglobin), and a longer financial incentive period. In this same trial, the adherence rate for the DFI alone arm was 70%; therefore the estimate of 80% adherence in the hybrid DFI/CHW arm seems reasonable. Using a two-sample comparison of proportions (usual care versus hybrid), we will require a sample size of 28 patients per arm to detect these differences with 80% power, assuming a Type I error rate of 0.05. Given the vulnerability and transience of this patient population, it is important to account for loss to follow-up, which we assume based on prior trials to be 20%. Therefore, we estimate that we will have to enroll 34 patients in each arm to end up with our minimal sample size. Our planned enrollment of 50 patients in each arm will easily allow us to meet this threshold. Our planned sample size will also allow us to detect a difference between DFI alone and hybrid arms (the secondary outcome), assuming the DFI arm has an adherence rate of 48% and the hybrid arm has a rate of 80%. In reality, we might see higher adherence than 48% in the DFI alone arm based on a prior similar trial as above in which the DFI arm had a 70% adherence. However, it is possible in this trial focusing on a vulnerable population, DFI alone may result in lower adherence. Missing data Efforts will be made to collect complete information on patients including 3 attempts to contact each patient via telephone and the provision of honoraria for completion of follow-up. We will check the medical record of those lost to follow-up and extract from the electronic medical record any relevant glycosylated hemoglobin that occurred within 4 weeks of the study completion date. We will track all missing values and assess the pattern of missing data and whether the missingness is non-ignorable. If appropriate, we will consider statistical methods such as multiple imputation.

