Data will be monitored by the Principle Investigator and other investigators throughout the data collection and analysis process. We will have an internal safety review that is blinded to arm and a quarterly discussion of adverse events. We will ask patients about any medical incidents and hospitalizations at the 3 and 6 month follow up visits and record their responses. A nurse practitioner will then determine if medical incidents and hospitalizations are study related. Study related events will be discussed with our internal DSMB.

The following documents are currently attached to this item:

There are no documents attached for this item.

Risk / Benefit Assessment

There is a very low ratio of risk to benefit in this study. There is minimal risk to participation in the study.

General Attachments

The following documents are currently attached to this item:

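### Hospitalisations are collected only by patient report at 3 and 6 months; the chart check already planned for lost patients should record admissions, emergency visits and deaths as well as HbA1c

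*Combined protocol and SAP*

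**What the plan says.** Four places in the combined protocol and SAP bear on this.

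- **Data and Safety Monitoring.** Events come from the participant: "We will ask patients about any medical incidents and hospitalizations at the 3 and 6 month follow up visits and record their responses". Next, "A nurse practitioner will then determine if medical incidents and hospitalizations are study related", and related events go to an internal DSMB. There is also an arm-blinded internal safety review and "a quarterly discussion of adverse events". No other source of medical incidents or admissions is named.
- **Subject compensation.** Under COVID-19 restrictions, adverse event screening at 3 and at 6 months is done by telephone and separated from the in-person data collection. It is still patient report at the same two time points.
- **Analysis Plan, Sample size calculations and Missing data.** The plan says it must "account for loss to follow-up, which we assume based on prior trials to be 20" percent. Staff make three telephone attempts per patient. For those lost, they check the medical record and "extract from the electronic medical record any relevant glycosylated hemoglobin that occurred within 4 weeks of the study completion date". Nothing else is to be taken from the record.
- **Procedures, Steps Eight and Nine.** The listed tasks at the two visits do not include an event question. Step Eight goes from downloading the glucometer log to "Provide the patient with a gift card. Follow up visit is concluded".

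The only surveillance between visits is the platform alert to a clinician for extreme glucose readings (Design; Procedures, Step Six). The documents do not say that these alerts are entered as adverse events.

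**The concern.** A patient who cannot be reached cannot report an admission, and nobody can self-report a death. Participants require insulin, have poorly controlled diabetes and live in high-poverty areas, and the Analysis Plan itself describes them as vulnerable and transient. Illness or admission is a plausible reason for missing a contact, so events may be more frequent among patients who are not asked than among those who are.

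At stake is how complete the information reaching the nurse practitioner and the internal DSMB is. They would see what retained patients recall, and a low event count could partly reflect who was available to answer. The gap is avoidable, because for the patients concerned the plan already has someone open the chart.

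**Working it through.** **1. The plan's own loss figure.** The 20% comes from the sample size calculation (40% against 80% adherence, 80% power, type I error 0.05; I take it as two-sided).

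- Without continuity correction: n = [1.96·√(2·0.6·0.4) + 0.8416·√(0.4·0.6 + 0.8·0.2)]² / 0.4² = (1.358 + 0.532)² / 0.16 = 22.3, so 23 per arm.
- With continuity correction: (22.3/4)·[1 + √(1 + 4/(22.3·0.4))]² = 27.1, so 28 per arm, as stated.
- Loss allowance: 28 × 1.20 = 33.6, so 34, as stated. The usual 28/0.80 gives 35. The one-patient difference has no bearing here.

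**2. Patients affected.** Planned enrolment is 150, 50 per arm (Accrual).

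- 0.20 × 150 = 30 in total; 0.20 × 50 = 10 per arm.
- If none of the 30 can be reached, all lack event data after their last contact.
- The number with no patient-reported event record at all is 30 minus those who completed the 3-month contact. The documents give no timing of loss, so this runs from 0 (all lost after that contact) to 30 (all lost before it).

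**3. Share of admissions missed.** No event rate appears in the documents, so these inputs are assumptions:

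- p = 15%, the proportion of retained patients admitted over the study.
- k = the admission rate in lost patients relative to retained patients (1 or 2).
- f = the fraction of a lost patient's events never asked about: 1 if lost before the 3-month contact; 0.5 if lost after it, with events spread evenly over the 6 months.

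Retained: 120 × 0.15 = 18 admitted. Lost: 30 × 0.15 × k, which is 4.5 (k = 1) or 9 (k = 2).

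| When lost | k | Missed | All | Share missed |
|---|---|---|---|---|
| All after 3-month contact | 1 | 2.25 | 22.5 | 10% |
| All after 3-month contact | 2 | 4.5 | 27 | 17% |
| All before 3-month contact | 1 | 4.5 | 22.5 | 20% |
| All before 3-month contact | 2 | 9 | 27 | 33% |

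In general the share is 0.20·k·f / (0.80 + 0.20·k). The 15% cancels, so it sets the counts but not the percentages. What drives the range is the timing of loss and the relative rate k.

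**4. Absolute numbers under other rates.** If 5%, 10%, 20% or 30% of the 30 lost patients were admitted, the expected number is 1.5, 3, 6 or 9. Even at 5%, the chance of at least one is 1 − 0.95³⁰ = 79%. These counts cover the whole study; only events after last contact go unrecorded.

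**The case against.** The strongest reply is that this is a sociobehavioural trial without an investigational drug or device, which the protocol rates as minimal risk, and that it is not without surveillance. Extreme glucose readings reach a clinician between visits, investigators monitor data throughout, and research assistants, CHWs and clinicians enter data directly into REDCap (Subject Confidentiality). The 20% is an allowance for the adherence outcome; with screening by telephone, a patient without glucometer or HbA1c data may still report events. All of this stands. It makes 30 an upper figure and keeps the point modest. It does not close the gap: the alerts cover glucose only, the REDCap route is not specified for adverse events, and telephone calls do not help with someone who cannot be reached.

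A reader might also infer more than the documents support:

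- **That staff do not ask about events at the visits.** Steps Eight and Nine omit the question, but Subject compensation names adverse event screening at both contacts, Step Nine includes a survey whose content is not shown, and an RA manual is cited but not available here. The omission is an inconsistency in the listed procedures.
- **That an early event could wait until after the 24-week study for review.** This requires adding the wait for the first question to a full quarter before the next discussion. The protocol places the nurse practitioner's determination after the response is recorded and does not tie it to the quarterly meeting.
- **That a safety comparison between arms would be biased.** No such comparison is planned: the analyses cover adherence and HbA1c, and the safety review is blinded to arm. Loss that differs by arm because of CHW contact is conjecture.

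**Conclusion.** The point holds as a gap in how events are found, and it is a cheap improvement rather than a flaw in the design. Following the plan as written, admissions after a lost patient's last contact go unrecorded, although that patient's chart is opened. With the assumed 20% loss this affects up to 30 of 150 patients. Between 10% and 33% of admissions would be missed, if lost patients are admitted at one to two times the rate of retained patients, events are spread evenly over time, and none of the 30 is reached by telephone. Neither the admission rate nor the timing of loss is in the documents. It would go too far to say that 30 patients have no safety record: that is the upper bound for patient-reported events, and glucose alerts may exist for some of them.

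**What to change.** - **Analysis Plan, Missing data.** When the medical record is checked for a patient lost to follow-up, also extract admissions, emergency visits and deaths from enrolment to week 24. Pass them to the nurse practitioner review described under Data and Safety Monitoring.
- **Preferably, do the same for all 150 participants** from the same source, so that finding an event does not depend on attending or answering the telephone.
- **Procedures, Steps Eight and Nine.** List the event screening that Subject compensation and Data and Safety Monitoring already rely on.

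The cost is modest abstraction time in one health system's record. An IRB modification may be needed, because Subject Confidentiality describes the research material as coming from surveys and glucometers. Admissions outside the health system would still be missed, so patient report should stay alongside the chart extraction. No treatment, endpoint or sample size changes.
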